8.4.1 Specific criteria for withdrawal (if applicable)

We accounted for potential dropouts in our sample size calculation.

8.5 Replacement of individual subjects after withdrawal

If a subject decides to discontinue participation before completing all study procedures, this subject will be considered a dropout and will be excluded from analyses. In case this happens during the recruitment period of the study, researchers may choose to replace

the subject. However, subject IDs will not be reused to prevent data confusion; instead, a new subject ID will be assigned to the “replacing” participant.

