4.4 Sample size calculation

There are no directly comparable studies available for an accurate sample size calculation, as previous research investigating the effect of tVNS on stress used different stimuli, making comparison challenging. However, previous research on the Maastricht Acute Stress Task (MAST) indicated that 85% of participants demonstrate a noticeable and quantifiable cortisol response (i.e., cortisol increase $\geq 2.5\text{nmol/l}$ from baseline) to the acute stress task (1). Anticipating that tVNS is expected to counteract the cortisol response to the MAST by 35%, resulting in an estimated 85% cortisol increase from baseline in the sham group vs. a 50% increase from baseline in the tVNS group, a sample size of 54 participants is required to detect this difference ($b=0.8$, $\alpha=0.05$). This estimate is consistent with other somewhat similar studies on tVNS. Based on previous experience with studies involving healthy volunteers, an additional six participants (10%) will be recruited to account for potential dropouts. This approach is deemed appropriate and feasible given the short and non-invasive nature of the intervention.

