10. STATISTICAL ANALYSIS

Demographic data and patient-reported data will be registered and saved in Castor by the coordinating investigator. Database cleaning will be carried out by the study coordinator and the local research nurses, using internal consistency checks and identification of database entries outside expected ranges.

Statistical analysis will be performed using IBM SPSS, R, Python, and Excel. Subject characteristics will be presented and analysed using descriptive statistics. Continuous parameters will be presented as means and standard deviations, and assessed between the two groups (taVNS vs. sham) with a two-sample unpaired t-test (for normally distributed data) or a nonparametric Mann-Whitney U test (for non-normally distributed data). Categorical variables will be represented as frequencies and analyzed using a Chi-square test or a Fisher's exact test. A p-value < 0.05 will be considered statistically significant.

Data interpretation will involve effect size estimates as appropriate for each statistical test (e.g. Cohen's *d* for t-tests, *f* for Mann-Whitney U test) as well as estimated intervals, such as 95% confidence intervals. Thereby, conclusions will not be drawn from a singular p-value alone. No missing data are expected. Primary and secondary outcomes data will be analysed based on an intention-to-treat approach.

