10.1 Primary study parameter(s)

The efficacy of taVNS in attenuating the acute stress response induced by the validated Maastricht Acute Stress Task (MAST) among healthy subjects will be determined based on cortisol levels in saliva samples, using an intention-to-treat principle. A repeated measures ANOVA will be utilized to evaluate both intergroup differences and within-group changes in cortisol levels across the different time points. If the assumption of normality is violated, a nonparametric equivalent will be employed. Multivariable regression analysis will be performed to correct for confounding effects of age, gender, and mental health (i.e. GAD-7, PHQ-9, BFI). Differences in cortisol saliva levels, with corresponding 95% confidence intervals (CIs) and two-sided p-values, will be calculated at a type I error level of 0.05.

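### Section 8.5 removes randomised participants who choose to stop early from the analysis, which contradicts the intention-to-treat analysis in sections 10 and 10.1

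*Protocol*

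**What the plan says.** Protocol section 8.5 sets the trigger, "If a subject decides to discontinue participation before completing all study procedures", and the consequence: "this subject will be considered a dropout and will be excluded from analyses". It continues "In case this happens during the recruitment period of the study, researchers may choose to replace" the subject, under a new ID. It gives no criterion for replacing and does not say who decides.

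The general part of section 10 states: "No missing data are expected. Primary and secondary outcomes data will be analysed based on an intention-to-treat approach". Section 10.1 repeats the principle for the primary outcome, which is to be judged "based on cortisol levels in saliva samples, using an intention-to-treat principle", by repeated measures ANOVA over the time points.

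Section 4.4 provides that "an additional six participants (10%) will be recruited to account for potential dropouts", and section 8.4.1 refers back to that allowance. Section 8.6 marks follow-up of withdrawn subjects as not applicable. Section 8.2 places randomisation after consent at visit 1 and before the test day.

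**The concern.** Sections 8.5 and 10 both fix who enters the primary analysis, and they fix it differently. This is not detail that a statistical analysis plan could fill in, because any such plan would have to override one of the two protocol statements. If 8.5 is followed, the trial reports a completers-only comparison under an intention-to-treat label.

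This could matter for the estimate. The MAST combines immersion of the hand in 4 °C water with mental arithmetic under negative feedback, and section 8.3.2 tells participants that they may withdraw from the task whenever they wish. Those who stop could differ in stress response from those who stay, and the stress response is what taVNS is meant to change. If so, the participants left in the two arms are no longer comparable in the way randomisation made them.

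**Working it through.** **1. Do the two rules apply to the same person?** Randomisation precedes the test day (section 8.2). Someone who chooses to stop during stimulation, the MAST or the saliva sampling is therefore already randomised. Section 8.5 excludes that person; sections 10 and 10.1 include them. The protocol gives no definition of intention-to-treat that reconciles the two.

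**2. How much is discarded?** Section 8.3.2 schedules eight saliva samples: baseline, pre-stress, and six from 5 to 55 minutes after the stressor. Leaving between the 45- and 55-minute samples means seven of eight have been given, and 8.5 drops all seven. The last blood pressure reading comes one hour after the MAST, so on a strict reading even a participant with all eight samples could be excluded for leaving before it.

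**3. The plan's own numbers.** Inputs: responder rates 85% (sham) and 50% (taVNS) from the Summary, two-sided alpha 0.05 (section 10.1), power 0.8 (section 4.4, written there as b). With the usual two-proportion formula without continuity correction, and mean proportion 0.675:

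n per arm = [1.96 × √(2 × 0.675 × 0.325) + 0.842 × √(0.85 × 0.15 + 0.50 × 0.50)]² / 0.35² = 26.9, rounded up to 27, or 54 in total.

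Allowing for 10% dropout: 54 / 0.90 = 60. Both stated figures reproduce. On the same rates, power is 80.2% with 27 per arm observed and 84.3% with 30 per arm observed. The planned loss is already covered, so replacement is not needed for power at that loss.

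**4. Illustration of possible bias.** Assumption, not in the documents: every dropout would have been a cortisol responder. If an arm with true rate p loses a fraction d of its participants, the rate among completers is (p − d) / (1 − d). At d = 0.10:

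- Sham: (0.85 − 0.10) / 0.90 = 83.3%
- taVNS: (0.50 − 0.10) / 0.90 = 44.4%

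Completers-only difference, against a true 35.0 points:

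| Loss | Sham only | taVNS only | Both arms |
|---|---|---|---|
| 5% | 34.2 | 37.6 | 36.8 |
| 10% | 33.3 | 40.6 | 38.9 |
| 20% | 31.3 | 47.5 | 43.8 |

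With no true effect (85% in both arms), a one-arm loss of 5%, 10% or 20% gives a false difference of 0.8, 1.7 or 3.8 points.

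The bias can go either way. These figures use the responder rates behind the sample size. The primary analysis is of cortisol levels over time, for which the protocol gives no standard deviation, so the corresponding shift in means cannot be derived.

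**The case against.** The best reply is that this is a wording conflict in a short, low-burden trial. There is one test session of two to three hours, payment depends on completion, and dropout may be small. No stated figure is wrong. Those who leave between visit 1 and the test day have no cortisol data, so excluding them from the cortisol analysis loses no measurements. The sentence about missing data can be read as referring to people who complete the session. All of this limits the likely size. It does not remove the contradiction.

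The reply also rules out several stronger readings that a reader might infer:

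- **That stopping is known to depend on the cortisol response.** No section says so; it is a plausible inference. The right described in 8.3.2 is to withdraw from the task, whereas 8.5 concerns leaving the study.
- **That the bias is a large share of the detectable effect.** This would need exactly the strongest responders to leave, from one arm only, and a standardised effect that the protocol does not state.
- **That the unblinded researcher picks replacements.** One test-day researcher knows the allocation, but the protocol does not say who decides on replacement. Allocation runs through central software with a sealed list, and nothing suggests that staff could choose a replacement's arm. Exclusion is automatic; only adding a replacement is discretionary, and only during recruitment.
- **That everyone who stops is excluded.** Section 8.5 covers participants who themselves decide to stop. It does not say how those withdrawn by the investigator under 8.4 are analysed.
- **That single missed samples will remove a stated share of participants.** The protocol gives no sample failure rate.

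A mixed model is also not a full cure. Someone who leaves the study during the MAST has at most the baseline and pre-stress samples. If leaving depends on the unobserved cortisol response, bias remains.

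**Conclusion.** The point stands as a direct contradiction between section 8.5 and sections 10 and 10.1 over who is in the primary analysis, together with a replacement rule that has no criterion. It should be resolved before unblinding.

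Bias from a completers-only comparison is possible but not established. Under the assumption that all dropouts are responders, a 10% loss in one arm moves the 35-point difference down by 1.7 points (sham) or up by 5.6 (taVNS), and produces 1.7 points where there is no effect. Other patterns of stopping would give other answers. The sample size is not affected.

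**What to change.** - **Section 8.5:** delete the exclusion sentence. Let replacements be added without removing the original participant, with the decision made by someone blinded to allocation.
- **Sections 10 and 10.1:** analyse all randomised participants in their allocated arm, using every available cortisol sample in a likelihood-based mixed model. This takes the place of repeated measures ANOVA, which in its classical form uses only participants with complete series. Section 10.2 already plans mixed models for the autonomic outcomes.
- **Label:** if participants who never started stimulation are left out, call the set modified intention-to-treat.
- **Sensitivity analyses:** keep the completers-only comparison as one. Add another for participants with no post-stress sample, since the mixed model alone does not protect against leaving that depends on unobserved cortisol.
- **Missing data:** replace the statement that none is expected with wording that fits the 10% dropout allowance in section 4.4.
- **Reporting:** give withdrawals by arm and by timing.

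The cost is a protocol amendment to the wording of 8.5, 10 and 10.1 and a change of model. No extra participants are needed: 54 and 60 stay as they are.

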8.6 Follow-up of subjects withdrawn from treatment

Not applicable.

8.7 Premature termination of the study

There are no expected reasons for premature termination of the study. However, in the event of urgent medical issues arising during the study (for example SAEs that result in death or are life threatening) the investigator (if necessary, together with the medical committee) can decide to halt the study to check whether it is safe to proceed or if termination is preferred.

9. SAFETY REPORTING

9.1 Temporary halt for reasons of subject safety

In accordance to section 10, subsection 4, of the WMO, the sponsor will suspend the study if there is sufficient ground that continuation of the study will jeopardise subject health or safety. The sponsor will notify the accredited METC without undue delay of a temporary halt including the reason for such an action. The study will be suspended pending a further positive decision by the accredited METC. The investigator will take care that all subjects are kept informed.

9.2 AEs, SAEs and SUSARs

9.2.1 Adverse events (AEs)

Adverse events are defined as any undesirable experience occurring to a subject during the study, whether or not considered related to transcutaneous vagal nerve stimulation or the MAST. All adverse events reported spontaneously by the subject or observed by the investigator, or his staff will be recorded. Subjects are promptly asked to report any changes in their health in the 24 hours following the test day via phone or email to the coordinating investigator. These adverse events will then be recorded in Castor.

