8.1.2 Secondary study parameters/endpoints

- Subjective stress responses to the MAST following taVNS or sham treatment, assessed through scores on the I-PANAS-SF and 0-100 Visual Analog Scales (VAS);
- Autonomic response to stress following taVNS or sham treatment and the MAST, assessed using a combination of a blood pressure monitoring, FitBit smartwatch, and the Shimmer3 GSR sensor;
- Stress responses in relation to potential affective symptoms and personality traits, using the GAD-7, PHQ-9, and BFI;
- Number and severity of adverse events.

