8.2 Randomisation, blinding and treatment allocation

After confirming suitability for inclusion and obtaining written informed consent during the initial visit, participants will be scheduled for a second visit (referred to as the test day). Prior to this test day, an independent investigator will randomise the subjects in a 1:1 parallel fashion to receive either taVNS or sham stimulation. The randomisation of participants will be conducted using an online environment provided by the CTCM (TENALEA) software. The concealment list will be generated by the CTCM and provided to a co-worker in the same department as the coordinating investigator. For emergencies, drs. [name] will be provided with the concealment list and will be able to de-blind. The concealment list provides information on which participant will get active taVNS and who will get sham stimulation. This information will not be given to the investigators, and the concealment list will be sealed until after the initial analysis.

In this study, blinding procedures will be implemented. The tVNS device used will be identical for both the active and sham groups, and the ear electrodes will be placed at the same anatomical location. Furthermore, the device will blink in both groups to ensure that participants remain blinded to their treatment allocation. The only differences are that the sham group will receive a device with a non-conducting electrode, and that the electrodes for the taVNS and sham groups will be slightly different. Consequently, the investigator placing the electrodes will be aware of the treatment allocation. To maintain proper blinding, two researchers will be involved on the test day. One researcher will manage the tVNS stimulation and will be responsible for programming the devices, while the other researcher will conduct the second part of the test day, the Maastricht Acute Stress Task (MAST). This division ensures that the researcher conducting the MAST and responsible for data analysis is blinded to the treatment allocation.

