e. Analysis of potential effect

The tVNS device is considered safe. Previous studies have shown no serious or long-lasting adverse events (34, 41-43). See paragraph 6.4 'summary of known potential risks and benefits' for previously reported risks.

f. Pharmacokinetic considerations

Not applicable.

g. Study population

All participants are healthy volunteers aged 18-65 years. No risks have been identified for this population (see also paragraph 6.2). Vagus nerve stimulation has been applied to both healthy controls and patient populations for several years (55-58).

h. Interaction with other products

Not applicable.

i. Predictability of effect

Not applicable.

j. Can effects be managed?

In healthy humans, taVNS has been demonstrated to be a safe and well-tolerated procedure, particularly in individuals without a history of cardiac disease (31, 41, 42). Subjects with cardiac pathology or pacemakers will be excluded from the study. However, autonomic parameters will be monitored continuously throughout the entire taVNS stimulation period and after the MAST. No serious complications have been reported in literature. A few subjects have reported dizziness, fatigue, concentration problems and a tingling sensation at the ear, which are typically associated with longer stimulation durations or with higher stimulation intensities (43). Therefore, prior to the experiment, the stimulation current will be adjusted according to each subject's sensitivity to ensure it remains below the pain threshold. Participants are allowed to withdraw from the study at any time.

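### Adverse events are a secondary endpoint, but the protocol states no standard enquiry or severity rating for the test day, and the researcher running the stimulation knows the allocation

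*Protocol*

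**What the plan says.** Section 8.1.2 lists "Number and severity of adverse events" among the secondary endpoints.

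Section 9.2.1 is where the protocol says how events reach the database. For the test day it states: "All adverse events reported spontaneously by the subject or observed by the investigator, or his staff will be recorded". It then adds a request made to everyone: "Subjects are promptly asked to report any changes in their health in the 24 hours following the test day". Participants make that contact themselves, by phone or email to the coordinating investigator. The section gives no standard question, no fixed time of enquiry and no severity scale.

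The effects to expect are already named. Section 13.1 (item j) says: "A few subjects have reported dizziness, fatigue, concentration problems and a tingling sensation at the ear". Section 6.4 adds headache, redness around the stimulation site, drowsiness with long-term use and slight hearing impairment on the electrode side.

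On blinding, Section 8.2 says of the sham and active electrodes: "Consequently, the investigator placing the electrodes will be aware of the treatment allocation". It divides the test day between two people: "One researcher will manage the tVNS stimulation and will be responsible for programming the devices", while a second person runs the stress task. It concludes: "This division ensures that the researcher conducting the MAST and responsible for data analysis is blinded to the treatment allocation". Section 5.1.2 states that participants are unaware of what they receive.

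**The concern.** An endpoint that counts and grades mild symptoms depends on how people are asked about them. Most of the expected effects are felt rather than seen, so an observer will miss many of them, and a participant who has just gone through a stress task may not think a tingling ear worth mentioning. The one request made to every participant is general, and it points at a period after these effects should mostly have passed.

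During the 30 minutes of stimulation, when the effects are most likely, the person in charge knows the arm. What that person notices, writes down or grades could differ between arms without anyone intending it. At stake is whether the endpoint can describe tolerability at all. The primary cortisol analysis is not affected.

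This is a matter of data collection. An analysis plan cannot recover events that were not elicited.

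**Working it through.** The protocol gives no adverse event rate, power or target precision, so there is no figure to reproduce. The check compares sections and then illustrates the mechanism on assumed values.

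**1. Timing of the general request against timing of the effects.** Inputs: the stress task lasts 5 + 10 = 15 minutes and follows stimulation (Sections 3 and 8.3.2); the last saliva sample is 55 minutes after the stressor ends, and recording continues to 60 minutes (Section 8.3.2).

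- If the task starts directly after stimulation, the last sample falls 15 + 55 = 70 minutes after stimulation ends.
- The earliest departure is 15 + 60 = 75 minutes after stimulation ends.
- Section 6.4 reports fatigue, concentration problems and tingling subsiding after 90 minutes in a pilot study, without saying from when the 90 minutes run. Section 13.2 says symptoms typically disappear quickly once the device is removed.

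The period in which these effects would occur is therefore mostly spent on site, where the stated routes are spontaneous report and staff observation. The 24-hour request comes after it, whether it is read from departure or from the end of the test day.

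**2. Where the blind protects the endpoint and where it does not.**

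- Participant self-report: stated to be blinded.
- Observation by the stress-task researcher: stated to be blinded.
- Observation, note-taking or grading by the researcher managing stimulation: unblinded.
- Receipt of the 24-hour reports by the coordinating investigator: the protocol does not say whether this person is the unblinded researcher.

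**3. Illustration on assumed values, 30 per arm (60 randomised 1:1).** Observed risk = true risk × fraction detected. The true risks and detected fractions below are assumptions, not protocol figures.

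| Case | True risk, taVNS / sham | Detected, taVNS / sham | Observed | Difference |
|---|---|---|---|---|
| A | 30% / 30% | 80% / 50% | 0.30 × 0.80 = 24%; 0.30 × 0.50 = 15% | 9 points, all spurious (7.2 v 4.5 expected cases) |
| B | 40% / 20% | 50% / 50% | 20%; 10% | true 20 points becomes 10 |
| C | 30% / 30% | 50% / 50% | 15%; 15% | none |

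Power for case B uses the usual two-sided 5% comparison of proportions, z = (d − 1.96·√(2p̄(1−p̄)/n)) / √([p₁(1−p₁)+p₂(1−p₂)]/n):

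- Full detection: (0.20 − 1.96 × 0.1183)/0.1155 = −0.28, power about 39%.
- Half detection: (0.10 − 1.96 × 0.0922)/0.0913 = −0.88, power about 19%.

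Case C shows that equal under-counting does not create a difference where there is none. Case B shows that it shrinks a real one. Case A needs unequal detection, and it is extreme in applying the gap to the whole count, whereas the unblinded route covers part of it.

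**The case against.** The best case for the protocol has four parts.

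- **Participants are asked.** Section 9.2.1 makes a general request to everyone. Section 11.4 says they are told the risks beforehand, and Section 11.2 has them restate these in their own words. A reader might infer that nobody is ever asked about their health, and that is wrong. What is missing is a standard, symptom-specific enquiry that covers the time on site.
- **Most expected effects are invisible to an observer.** They must therefore come from the participant, who is stated to be blinded, and Section 9.2.1 says all reported events are recorded. This stands, and it limits observer bias to visible events such as redness and to how the unblinded researcher records or grades a report. A reader might infer that the whole arm comparison lies outside the blind; the documents do not support that. Nor do they establish that self-reports are biased because active stimulation can be felt. Sections 3 and 8.3.2 describe stimuli below threshold and Section 5.1.1 describes intensity above threshold; those passages must be reconciled, but they settle nothing here.
- **No safety objective or between-arm test is planned.** Section 2.2 has no tolerability objective and Section 10.2 has no adverse event analysis. Grading and form details may sit in an analysis plan or case report form not at hand. This lowers the stakes. The collection method stated in Section 9.2.1 nevertheless remains as described.
- **The session is short, non-invasive and in healthy volunteers.** True, and this is why the remedy should be small.

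It is also tempting to take an upper confidence limit for zero events in 30 and inflate it by a capture fraction. The protocol plans no such limit and gives no source for a capture fraction, so that figure would have no footing.

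**Conclusion.** The point holds as a cheap improvement to data collection. Nothing in Section 9.2.1 is contradictory, but its stated method is weak for an endpoint defined by number and severity.

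Two consequences follow. Counts are likely to be low, an inference from passive on-site capture of mild and short-lived symptoms. Staff-observed events, and any grading by the researcher managing stimulation, are open to observer bias. Neither can be sized from the documents. The 9-point spurious difference and the halving of a real one in the illustration rest wholly on assumed risks and detected fractions.

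**What to change.** In Section 9.2.1, add one short self-completed form in Castor, identical in both arms. It should list the effects named in Sections 6.4 and 13.1 (item j), with a severity rating for each and a free field for anything else. Participants complete it twice: after the last saliva sample, asking about the whole period since stimulation began, and once by emailed link at 24 hours. Name this form as the source for the Section 8.1.2 endpoint, with spontaneous and observed events kept as an addition.

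Two safeguards belong with it.

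- Do not show the symptom list just before stimulation, because it could cue ear sensations ahead of a sham whose blind depends on sensation, and ahead of the stress task. Placing the form after the last sample also means it cannot affect the cortisol measurements.
- Withhold the responses from the blinded stress-task researcher, who is also responsible for the analysis, until the primary analysis is done; reports of tingling could hint at the arm. Someone else on the team reads them for safety.

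The cost is a few minutes per participant, one extra form in a system already in use, and a protocol amendment. Recorded counts will be higher and will not be comparable with rates from studies that relied on spontaneous reports, which the study report should say.
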